5.1 Analysis of the Primary Immunogenicity Objective

The planned analysis will compare $Y = \text{sum of CEs recognized by CD4 and CD8 T cells at week 26 minus the number at baseline}$ between the p24CE/full-length Gag DNA and placebo arm, using a two-sided 5% level Wilcoxon rank-sum test, which is anticipated to have greater statistical power than analyzing the binary version of whether $Y > 0$, for which statistical power was based.

An exact 95% confidence interval (CI) for the median of all paired differences between observations in the two arms (i.e., Hodges-Lehmann estimate) will be calculated to provide additional insight on the effect of p24CE/full-length Gag DNA vaccine. Comparisons will also be made between the Gag DNA alone vaccine arm and each of the other arms in the same manner.

The primary immunogenicity analysis for this pilot study will be per protocol, limited to participants who received all four study vaccination/placebo administrations and who did not take any medication prohibited by the study protocol on or prior to their week 26 visit. Since the amount of missing data is expected to be low in this study, the primary comparison will be based on the complete case analysis, i.e., remove records with missing data.

The following sensitivity analyses will be carried out to measure the robustness of the study findings:

- Using the stratified Wilcoxon (Van Elteren) test adjusting for the stratification factor.
- Using modified ITT approach for the primary comparison.
- Excluding the data from participants with delayed #2 and/or #3 vaccination injection due to the COVID -19 pandemic.

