Analysis will be performed in a superiority framework, comparing between arms the change in the number of CEs with a CD4 and/or CD8 T cell response from baseline to week 26.

Major change of the study follow-up

Due to the feasibility challenges posed by the COVID-19 situation, Clarification Memo #2 was issued to broaden the visit window from ± 14 days to -14 days to +60 days, starting from 03/16/20. On April 8 2020, after further review, Letter of Amendment #3 was then issued to further broaden the visit window from +60 days to +180 days but sites were still encouraged to schedule the applicable visits within +90 days.

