2.3.1 Primary Objective

1. To compare the additional number of p24CEs recognized by a CD4 and/or CD8 T cell response in participants at each study arm at week 26 compared to baseline
2. To evaluate the safety of the p24CE/full-length Gag DNA vaccine and the full-length Gag DNA vaccine in HIV-infected persons receiving ART.

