3.1 Primary Outcome Measures

3.1.1 Immunogenicity

The number of CEs with a CD4 and/or CD8 T cell response at week 26 compared to baseline in an individual study participant. A CE response (for a participant at a given time point) is defined by a criterion (Horton et al., J Immunol Methods. 2007) that uses Fisher's exact test to compare the proportion of peptide-stimulated CD4 and/or CD8 T cells that are cytokine positive to the proportion that are cytokine positive in the unstimulated sample (negative control), and applying a stringent p-value of 10e-5 as a cutoff.

NOTE: The number of CEs with a CD4 and/or CD8 T cell response will be provided by [name] lab.

NOTE: For this primary outcome, we will sum the CD4 and CD8 responses.

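### The primary variable sums CD4 and CD8 recognitions, so it can rise without any additional CE being recognised, and no 5.1 sensitivity analysis counts distinct CEs

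*SAP*

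**What the plan says.** Three places in the SAP read as a count of CEs in which each CE counts once, whichever cell type recognises it:

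- 2.3.1, primary objective 1: "To compare the additional number of p24CEs recognized by a CD4 and/or CD8 T cell response".
- 2.1, the statement of the planned comparison: "the change in the number of CEs with a CD4 and/or CD8 T cell response from baseline to week 26".
- 3.1.1, opening sentence of the outcome: "The number of CEs with a CD4 and/or CD8 T cell response at week 26 compared to baseline in an individual study participant".

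Two places add the cell types together:

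- 3.1.1, second note: "For this primary outcome, we will sum the CD4 and CD8 responses".
- 5.1, the definition of Y: "sum of CEs recognized by CD4 and CD8 T cells at week 26 minus the number at baseline".

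The first note in 3.1.1 says of the laboratory data: "The number of CEs with a CD4 and/or CD8 T cell response will be provided by" a named laboratory. So the section describes an and/or figure being delivered and then a sum being analysed.

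Section 5.1 compares Y between arms with a two-sided 5% Wilcoxon rank-sum test and a Hodges-Lehmann estimate with exact 95% interval. Its three sensitivity analyses are a stratified (Van Elteren) test, a modified ITT population, and exclusion of participants with COVID-delayed second or third injections. Section 5.3 adds a binary secondary analysis, the percentage of participants responding by CD4 and/or CD8 to more CEs at week 26 than at baseline, and then the same for each cell type.

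**The concern.** A sum over cell types and a count of distinct CEs are different quantities. If a participant's CD8 cells already recognise a CE at baseline and the vaccine adds a CD4 response to that CE, the sum rises by one but no further CE has been recognised.

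What is at stake is interpretation. Objective 1 asks about additional CEs. A positive primary test could reflect broader recognition, a second cell type joining responses that already existed, or a mixture. The listed sensitivity analyses change the test or the participants and never the count, so none of them separates these explanations.

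**Working it through.** **1. The plan's own figure.** Inputs from SAP 2.1: 20 v 10 in the main comparison, 10% inflation for loss, 0.64 v 0.10, two-sided Fisher's exact test at 5%, 80% power. Removing 10% leaves 18 v 9. Power is the sum, over all tables (x, y) with Fisher p ≤ 0.05, of Bin(x; 18, 0.64) × Bin(y; 9, 0.10) = 0.798. For 0.85 v 0.30, p24CE against full-length Gag, it is 0.794. Total size: 36 / 0.9 = 40. The stated power reproduces, so this point is not about a sample-size error.

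**2. How the two counts relate.** For one participant at one visit:

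CD4 count + CD8 count = distinct CEs + CEs recognised by both.

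Taking week 26 minus baseline:

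Y(sum) − Y(distinct) = change in the number of CEs recognised by both.

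The two agree only when that change is zero. On this reading Y(sum) is also the change in secondary outcome 1 plus the change in secondary outcome 2 of SAP 3.2.

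**3. Two constructed participants.**

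| | Baseline | Week 26 | Y(sum) | Y(distinct) |
|---|---|---|---|---|
| A | CD8 to CEs 1, 2 | CD4 and CD8 to CEs 1, 2 | 4 − 2 = +2 | 2 − 2 = 0 |
| B | CD4 and CD8 to CEs 1, 2 | CD8 to CEs 1, 2, 3 | 3 − 4 = −1 | 3 − 2 = +1 |

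The two versions can differ in size and in sign.

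**4. Effect on the test (assumed data, illustration only).** Take 18 v 9. Suppose 8 vaccinees and no placebo participant add a second cell type to one already recognised CE, and nothing else changes. Then Y(sum) is +1 in those 8 and 0 in the other 19, and Y(distinct) is 0 in all 27. With only two values, the exact rank-sum distribution is hypergeometric in X, the number of the eight +1 values that fall in the vaccine arm. Its mean is 8 × 18/27 = 5.33, and the observed value is 8, a deviation of 2.67.

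- Upper tail: C(18,8)/C(27,8) = 43,758/2,220,075 = 0.0197.
- Lower tail at least as far from the mean (X ≤ 2): (9 + 648 + 12,852)/2,220,075 = 0.0061.
- Exact two-sided p = 0.0197 + 0.0061 = 0.026. Doubling the upper tail gives 0.039.

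With 7 v 0 the p-value is 0.059. If one placebo participant shows the same change, 10 vaccinees are needed (p = 0.042, or 0.065 with the doubled tail).

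**5. What else the plan would show in the 8 v 0 case.** Of 18 × 9 = 162 between-arm pairs, 8 × 9 = 72 differ by +1 and 90 by 0, so the Hodges-Lehmann estimate is 0. A 5.3 responder defined on distinct CEs would show 0/18 v 0/9.

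**6. What 5.3 can settle.** It is binary, so it ignores how many CEs were gained. It does not say whether its and/or responder is counted once per CE or by the sum. The separate CD4 and CD8 analyses cannot recover the overlap between them.

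**The case against.** The strongest reply is that the primary variable is defined. The note in 3.1.1 gives a rule specific to this outcome, and 5.1 applies it. A reader might infer that the plan leaves its primary variable unspecified, but the documents do not support that. The sum is prespecified and disclosed, and double counting follows from it on the plain reading. What is missing is an explicit sentence, and agreement with the wording elsewhere.

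The sum may also be deliberate. The hypothesis in 2.2 concerns newly induced responses, and a new CD4 response to a CE already seen by CD8 cells is one. That stands as a reason to keep the sum. It does not make the sum an answer to objective 1 as worded.

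A reader might further infer that power rests on one count and the 5.3 responder on another, since 5.1 describes the binary version of Y > 0 as the one "for which statistical power was based". This is unproven. Section 5.3 gives no counting rule, and the and/or phrase alone does not settle it, because 3.1.1 uses the same phrase and then prescribes a sum. Section 2.1 speaks only of increased CE responses, which fits either count.

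Finally, the illustration is extreme, and the plan would partly expose it through the Hodges-Lehmann estimate of 0 and, if based on distinct CEs, the 5.3 responder. This is accepted. In a mixed case, with some new CEs and some added second cell types, those checks would be much less clear.

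**Conclusion.** The point holds as a mismatch between what the primary test measures and what objective 1 asks. A significant result on the sum need not mean that more CEs were recognised, and no 5.1 sensitivity analysis addresses this. It should be fixed because the remedy is cheap and bears on how the primary result is read.

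The size in this trial cannot be derived: the documents reviewed give neither the number of CEs nor the overlap between CD4 and CD8 recognition. The 8 v 0 example (p = 0.026 at 18 v 9) rests wholly on assumed data and shows that the counts can disagree, not how likely that is. Nothing here implies an inflated type I error or a wrong sample size.

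Two documents could narrow the point. The Analysis Implementation Plan, which the SAP's introduction names as the place for coding descriptions, and protocol section 10.2.1, which SAP section 3 cites for the outcomes, were not available for this review.

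**What to change.** 1. Keep the prespecified sum as primary unless the sponsor confirms that the distinct count was intended. In that case, redefine Y and keep the sum as supportive.
2. If the sum stays, state in 3.1.1 and 5.1 that a CE recognised by both cell types counts twice.
3. Make 2.1, 2.3.1, 3.1.1 and 5.1 agree, in line with the protocol objective and protocol section 10.2.1. As the SAP takes its objectives and outcomes from the protocol, check whether the protocol wording must change too.
4. Add to 5.1 a named sensitivity analysis of the change in distinct CEs (CD4 and/or CD8), with the same Wilcoxon test and Hodges-Lehmann interval.
5. State which count the 5.3 and/or responder uses.

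The cost is some wording and one extra analysis. The distinct count has a narrower range and so more ties, and it gives no credit for a second cell type added to a CE already recognised; both are acceptable in a sensitivity analysis. No new assay is needed, since 3.1.1 defines response for each CE, but per-CE results must be requested if the laboratory supplies only CD4 and CD8 totals. The change should precede the database freeze and unblinding, so that the choice of count cannot look data-driven.

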This Primary Statistical Analysis Plan (SAP) describes the primary and secondary outcome measures and general analytic approaches of ACTG A5369 that will be included in the primary manuscript or submitted to ClinicalTrials.gov. It has been developed to facilitate discussion of the statistical analysis components amongst the study team; and to provide agreement between the study team and statisticians regarding the statistical analyses to be performed and presented in the Primary Statistical Analysis Report (SAR). Detailed outlines of tables, figures, and coding descriptions that will be included in the Primary SAR are included in the Analysis Implementation Plan (AIP). A separate SAP for Other Objectives will be developed when results for the Primary and Secondary Objectives are known, and analyses will be presented in a separate report. Data for the Primary SAR will be downloaded once the last participant has completed 48 weeks of follow-up, all queries have been resolved, and the database frozen for analysis. The Primary SAR will be used for submission of results to ClinicalTrials.gov. Results for primary outcomes are required to be submitted within one year of the primary completion date (PCD), which is the date that the final participant is examined for the purposes of final collection of data for all of the primary outcomes. The primary immunogenicity outcome is measured at 26 weeks of participant follow-up, and the primary safety outcome data collection is completed at 48 weeks of follow-up. Thus, the PCD of this study is based on 48 weeks of follow-up. Results for secondary outcome measures for this study are due at the same time.

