2.1 Study Design

A5369 is a phase I/IIa, randomized, double-blind, placebo-controlled study that will evaluate the safety, immunogenicity, and preliminary assessment of efficacy of a novel vaccine encoding “conserved elements” (CE) of the HIV-1 Gag core protein, p24Gag, as a therapeutic vaccine in HIV-1 infected persons on antiretroviral therapy (ART) with the aim to induce potent virus-specific cytotoxic T lymphocytes (CTL) responses. The primary efficacy outcome will be based on HIV-specific immunologic assays at baseline and week 26.

Duration

Participants will be on study for a total of 48 weeks.

Sample Size The target sample size of 40 (20 p24CE; 10 full length Gag; 10 placebo) for the randomized arms is selected to detect a 0.54 difference in the probability that a participant has increased CE responses (0.64 for p24CE vaccine and 0.10 for placebo) between arms based on a two-sided Fisher's exact test with 80% power, 5% alpha level, and 10% inflation of the estimated sample size for loss-to-follow-up or unusable laboratory specimens. The study also has approximately 80% power to detect a difference of 0.85 versus 0.30 when comparing the p24CE and full-length Gag vaccine arms.

Population

HIV-infected individuals receiving ART with plasma HIV-1 RNA <50 copies/mL for at least 2 years (one “blip” allowed), current CD4 T cell counts >500 cells/mm³, and nadir CD4 T cell counts >350 cells/mm³ (by documentation or candidate recall).

Randomization and Stratification

Participants will be randomized 2:1:1 to the p24CE/full-length Gag DNA vaccine arm versus full-length Gag DNA vaccine arm versus placebo arm using the permuted block method.

Randomization will be stratified by indication of willingness to have the leukapheresis procedure at study screening. The active vaccines/placebo will be administered by intramuscular injection/electroporation.

Regimen

Arm 1: p24CE/full-length Gag DNA Vaccine Arm

p24CE1/2 pDNA 4 mg administered by injection/electroporation at week 0 and week 4. Then p24CE1/2 pDNA 2 mg admixed with full-length p55gag pDNA 2 mg administered by one injection/electroporation at week 12 and week 24.

Arm 2: Full-length Gag DNA Vaccine Arm

Full-length p55gag pDNA 4 mg administered by one injection/electroporation at week 0, week 4, week 12 and week 24

Arm 3: Placebo Arm

Placebo (Sodium Chloride for Injection, USP 0.9%) 1 ml administered by one injection/electroporation at week 0, week 4, week 12 and week 24.

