5.3 Analysis of the Secondary Objectives

The percentage of participants in each study arm with a CD4 and/or CD8 cell response to an increased number of CEs at week 26 compared to baseline will be presented along with an exact binomial 95% CI. Pairwise comparisons among study arms will be conducted using Fisher's exact test. Similar analyses will be performed for CD4 and CD8 cell responses separately.

The absolute change in total magnitude of CD4 T cell responses against each CE added together among study arms will be compared using the two-sided Wilcoxon rank-sum test. The analysis for CD8 T cell responses will be conducted in the same manner. All statistical tests will be two-sided at the 5% nominal level of significance without adjustment for multiple testing.

6 Report components

Detailed descriptions of the content of each of the following sections are given in the AIP.

1. Study entry
 - a. Screening
 - b. Accrual
 - c. Eligibility and stratification errors
2. Baseline characteristics
3. Protocol deviations
4. Study and treatment status
5. Primary immunogenicity outcome
 - a. Evaluability
 - b. Primary immunogenicity outcome
 - c. Sensitivity analyses
6. Safety:
 - a. Primary safety outcome
 - b. Deaths
 - c. Overall safety
7. Secondary Outcomes

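### Does SAP section 5.1 need to say whether the primary Wilcoxon p-value is exact or a normal approximation?

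*SAP*

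**What the plan says.** SAP section 5.1 defines Y as the summed CD4 and CD8 count of recognised conserved elements at week 26 minus the count at baseline. It compares Y between the p24CE arm and placebo "using a two-sided 5% level Wilcoxon rank-sum test". The paragraph that follows adds "An exact 95% confidence interval (CI) for the median of all paired differences between observations in the two arms". It then extends the method to the third arm: "Comparisons will also be made between the Gag DNA alone vaccine arm and each of the other arms in the same manner".

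For the responder percentages, section 5.3 states "Pairwise comparisons among study arms will be conducted using Fisher's exact test". The Wilcoxon tests in section 5.3 carry no version either. The SAP text says nothing about ties or continuity correction.

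The SAP's introduction gives its purpose as "to provide agreement between the study team and statisticians regarding the statistical analyses to be performed and presented". The same introduction assigns coding descriptions to the Analysis Implementation Plan (AIP), and section 6 sends the detailed content of each report section there, including the primary immunogenicity outcome and its sensitivity analyses.

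**The concern.** The plan says exact for the interval and for Fisher's test, so its absence from the primary p-value is noticeable. Y is a difference of counts, and section 2.1 expects only 10% of placebo recipients to increase, so many values may tie at or near zero. In a small, heavily tied sample the exact and approximate p-values separate.

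Near the threshold, two analysts who both follow section 5.1 could then report opposite verdicts on the primary comparison. If nothing else fixed the choice, it could be made after unblinding. The silence carries over to the two comparisons with the Gag-alone arm and to the sensitivity analyses. There, a changed verdict might come from the p-value method and not from the change of population or stratification.

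**Working it through.** **Inputs.** From SAP section 2.1: 20, 10 and 10 randomised; 10% allowance for loss; responder rates of "0.64 for p24CE vaccine and 0.10 for placebo"; and a second power statement for "a difference of 0.85 versus 0.30 when comparing the p24CE and full-length Gag vaccine arms". Evaluable sizes are 20 × 0.9 = 18 and 10 × 0.9 = 9. The documents give neither the number of conserved elements nor the distribution of Y, so every disagreement rate below rests on assumed distributions.

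**The plan's own figure.** Enumerating both binomials with a two-sided Fisher test at 5%, 18 v 9 gives power 0.798 for 0.64 v 0.10 and 0.794 for 0.85 v 0.30. The stated 80% reproduces.

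**One dataset by hand: 7 of 18 v 0 of 9 gain, all gains equal, all others unchanged.**

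- Midranks: the 20 zeros get (1 + 20)/2 = 10.5 and the 7 gainers get (21 + 27)/2 = 24.
- Placebo rank sum W = 9 × 10.5 = 94.5. Null mean = 9 × 28/2 = 126. The difference is 31.5.
- Tie-corrected variance = (18 × 9/12) × [28 − ((20³ − 20) + (7³ − 7))/(27 × 26)] = 13.5 × (28 − 8316/702) = 218.1, so SD = 14.77.
- Normal approximation: z = 31.5/14.77 = 2.13, p = 0.033. With continuity correction, z = 31/14.77 = 2.10, p = 0.036.
- Exact, conditional on ties: let k be the number of placebo gainers, with null mean 7 × 9/27 = 2.33. P(k = 0) = C(18,7)/C(27,7) = 31,824/888,030 = 0.0358. Values at least as far away on the other side are k ≥ 5: (19,278 + 1,512 + 36)/888,030 = 0.0235. The sum is p = 0.059.

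If the seven gains are all different, the normal p is 0.036 to 0.039 and the exact p is 0.058.

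**Neighbouring results, no placebo gainers, gains all equal or all different.**

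| Gainers | Normal p | Exact p |
|---|---|---|
| 7/18 v 0/9 | 0.033–0.039 | 0.058–0.059 |
| 8/18 v 0/9 | 0.019–0.024 | 0.026–0.032 |
| 4/9 v 0/9 (Gag alone v placebo) | 0.028–0.034 | 0.082 |

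For p24CE v placebo, one extra gainer brings the two versions back into agreement.

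**Neither version is always the stricter.** With p24CE at −1 (one), 0 (nine), 1 (seven), 2 (one) and placebo all 0, exact p = 0.0486 and normal p = 0.051 to 0.054.

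**How often the verdicts differ (18 v 9; 20,000 simulated trials per scenario; Y assumed between −1 and 4).**

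| Responder rates | Exact and normal disagree |
|---|---|
| 0.64 v 0.10 (planned) | 1.2–1.5% |
| 0.40 v 0.10 (assumed) | 2.0–2.9% |
| 0.30 v 0.10 | 2.2–3.2% |
| no effect | 2.7–2.9% |

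In these runs the null rejection rate was 1.4 to 2.0% (exact) and 4.1 to 4.8% (normal). At the planned effect the exact test rejected in 76.9% of trials and the normal version in 76.6 to 77.9%.

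**Wider assumptions.** A second set of simulations (2,500 trials per scenario) varied the gain sizes and let 0 to 20% of each arm fall below baseline. Disagreement was 0.3 to 4.0% at 0.64 v 0.10. At 0.40 v 0.10 it was 7.5 to 9.0% when nobody fell and 0.5 to 4.1% when some did. For Gag alone v placebo at 9 v 9, taking 0.30 v 0.10, it was 1.7 to 8.0%. Type I error at 18 v 9 was 0.9 to 4.0% (exact) and 3.6 to 5.2% (normal). The simulation standard error near 5% is √(0.05 × 0.95/2,500) = 0.4 percentage points, so 5.2% is compatible with 5%.

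**The case for a change.** The strongest case for acting is that one sentence would settle the matter, and that the choice should be fixed in advance precisely because both versions are valid. The SAP exists to record agreement on the analyses, and the choice of inferential method arguably belongs there and not in a coding document. The examples need only integer ties. For Gag alone v placebo the two p-values are far apart (0.03 v 0.08).

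Part of this stands: the supplied text is silent, and the verdict can turn on the choice. It does not show that the choice is still open, because the AIP is where the plan puts such detail and it cannot be inspected here. Late selection of a version would require the AIP to be silent or written late, and nothing in the documents suggests either. Gag alone v placebo is not the main comparison, and section 2.1 gives no power for it.

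One related detail also stands. An exact Hodges-Lehmann interval built from the no-ties distribution can touch zero beside a significant p-value. In one checked dataset the exact p was 0.045 and that interval ran from 0 to 2. The SAP does not say that the interval will be built this way, and the same analysts would settle it when they code the test.

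**Conclusion.** The omission is real, but it is a detail that analysts can fill sensibly, and the plan is sound without it. Either version keeps the type I error at or below about 5%, and at the planned effect they have nearly the same power, so neither is a better method that the plan passes over. Disagreement is about 1 to 3% of trials in most scenarios. It reaches 8 to 9% only when an assumed weaker effect (0.40 v 0.10) is combined with no participant below baseline; at 9 v 9 it can reach 8.0% for the unpowered Gag-alone comparison. Section 5.1 describes a pilot study and section 5.3 uses nominal 5% tests without multiplicity adjustment, so a borderline p-value will not be read as confirmatory. The estimate and its interval will be reported beside it.

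This rests on assumed distributions of Y, on evaluable numbers near 18 v 9, and on the statisticians using one version throughout, which is ordinary practice and the kind of detail the AIP is meant to hold.

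### Does a Hodges-Lehmann interval that can stop at exactly 0 undercut a significant Wilcoxon test on the tied CE count?

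*SAP*

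**What the plan says.** The framework is set in SAP 2.1: "Analysis will be performed in a superiority framework, comparing between arms the change in the number of CEs" with a T cell response. SAP 3.1.1 adds "For this primary outcome, we will sum the CD4 and CD8 responses", so the outcome is a whole-number count at each visit and its change Y is a whole number too.

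SAP 5.1 makes a two-sided 5% Wilcoxon rank-sum test of Y the primary comparison, and expects it to have more power than a test of whether Y>0. It then adds "An exact 95% confidence interval (CI) for the median of all paired differences between observations in the two arms (i.e., Hodges-Lehmann estimate"), as a supplement that sheds further light on the vaccine effect. The same pairing is used for the comparisons involving the Gag-alone arm.

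The trial was sized on the binary version: "0.64 for p24CE vaccine and 0.10 for placebo" for the main comparison, and "a difference of 0.85 versus 0.30 when comparing the p24CE and full-length Gag vaccine arms". For that binary version SAP 5.3 gives the percentage in each arm with an exact interval, and "Pairwise comparisons among study arms will be conducted using Fisher's exact test".

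The SAP does not say how ties are handled in the test or the interval. Its introduction states that "coding descriptions that will be included in the Primary SAR are included in the Analysis Implementation Plan (AIP"), which is not among the documents.

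**The concern.** With continuous data, the exact Hodges-Lehmann interval is the inversion of the Wilcoxon test, so p<0.05 and a 95% interval excluding 0 go together. Ties break that link. Pairs with equal Y count as half in the test, but they sit at 0 in the ordered list of differences and hold the lower limit there.

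This is the only between-arm interval planned for the primary endpoint, in a superiority trial. A report of p=0.005 with an interval of 0 to 2 could be read as compatible with no effect. If many participants keep the same count from baseline to week 26, that could be the usual appearance of a positive result.

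**Working it through.** **Inputs.** "The target sample size of 40 (20 p24CE; 10 full length Gag; 10 placebo") and a 10% allowance for loss (SAP 2.1) give 20×0.9=18 and 10×0.9=9 evaluable. P(Y>0) is 0.64 v 0.10 (SAP 2.1). The test and interval are those of SAP 5.1. The distribution of Y beyond P(Y>0) is not given, so it is assumed and varied.

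**1. The plan's own figure.** Power of Fisher's exact test is the sum, over all (a, b) with two-sided p≤0.05, of Bin(a; 18, 0.64)×Bin(b; 9, 0.10). The result is 79.8%, against a stated 80%. For 0.85 v 0.30 it is 79.4%. Both reproduce.

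**2. The interval.** There are 18×9=162 pairwise differences. The exact limits are the k-th smallest and k-th largest, with k taken from the null distribution of U. At 18 v 9, k=43, with no-ties coverage 95.4%. The limits are therefore the 43rd and the 120th (162−43+1) ordered differences. The lower limit exceeds 0 only if at most 42 differences are 0 or less, so at least 162−42=120 pairs (74%) must strictly favour vaccine.

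**3. An illustration.** Vaccine Y: −1 (1 participant), 0 (5), 1 (5), 2 (4), 3 (3). Placebo Y: −1 (2), 0 (6), 1 (1).
- Pairs favouring vaccine: 5×2 + 5×8 + 4×9 + 3×9 = 113.
- Tied pairs: 1×2 + 5×6 + 5×1 = 37.
- Pairs favouring placebo: 162−113−37 = 12.
- 12+37=49 is at least 43, so the 43rd difference is 0. The estimate is 1 and the interval is 0 to 2.
- U with ties at half is 113+37/2=131.5, against a null mean of 162/2=81. The exact permutation p is 0.005.

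The two results agree once read correctly. At a shift of exactly 0 the test rejects (131.5 exceeds 120). At a shift just above 0 the 37 ties turn against vaccine, U drops to 113, and 113<120 does not reject. The interval found by inverting the test is open at 0: it reaches down to 0 but does not contain it.

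**4. How often.** The table is for p24CE v placebo, 18 v 9, 0.64 v 0.10. Shares are of significant trials favouring vaccine, by exact permutation p with ties. Ranges cover gains and losses of 1, 1-3 and 1-6, except that the unequal-decline row covers gains of 1 and 1-3. Power is for the tie-corrected Wilcoxon test; the choice of Wilcoxon p-value moves the shares by about 1 point.

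| Assumed Y | Lower limit exactly 0 | Wilcoxon power |
|---|---|---|
| All non-increasers at 0 | 86-89% | 78-80% |
| 70% of non-increasers at 0 | 53-70% | 70-76% |
| 50% of non-increasers at 0 | 35-66% | not tabulated |
| Declines 10% vaccine v 50% placebo | 35-52% | 85-88% |
| Rounded normal, SD 1, 2, 3 | 25, 9, 5% | 95-96% |

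If every change is 0 or +1, full enumeration gives 88.7%. With declines as large as 7, the 70% row falls to about 51%. For 70-100% at 0, the share is 54-88% at 20 v 10 and 56-90% at 16 v 8. In these simulations at 18 v 9 the lower limit was never below 0 in a significant trial, and the interval never excluded 0 when the test was non-significant.

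**5. The alternative.** One could report the difference in P(Y>0) with an exact unconditional 95% interval. In the illustration this is 12/18−1/9=0.56, interval 0.11 to 0.80. Over the scenarios at 0.64 v 0.10 it includes 0 in 0-5% of significant trials with equal declines, 9% with declines of 10% v 50%, and 15-16% under rounded-normal Y. It excludes 0 beside a non-significant Wilcoxon test in 1-13% of all trials.

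**The case for a change.** The strongest case for a change is this. The mechanism is arithmetic, not opinion. Inverting the tie-conditional exact test instead of using ordered differences still puts the limit at 0 in 52-85% of significant trials with 70-100% of non-increasers at 0, so it is not a quirk of one algorithm. SAP 5.3 gives intervals per arm and p-values between arms, but no interval for a between-arm difference. The effect measure is fixed in SAP 5.1, so the implementation plan cannot be assumed to replace it. A few sentences would avoid a foreseeable misreading. p24CE v Gag behaves similarly: at 0.85 v 0.30 with 70-100% at 0, the share is 74-80% with unit gains and 30-44% with gains of 1-6.

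The mechanism stands, and so does the absence of a second between-arm interval. Three things weaken the rest.

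- The high shares need 70% or more of non-increasers at exactly 0, which no document supports. In those scenarios the Wilcoxon test has 70-80% power against Fisher's 79.8%, while SAP 5.1 expects it to do better than the binary test. That expectation may be wrong. But the two scenarios with a clear gain in power give shares of 5-52%.
- The reader is not left with a bare interval. With 70% at 0, the Hodges-Lehmann estimate is above 0 in over 99% of significant trials. It would stand beside p<0.05 and the SAP 5.3 percentages.
- The replacement drops the size of gains and losses, which SAP 5.1 deliberately chose to use, and at SD 2-3 it does worse than Hodges-Lehmann. Its mismatch can also run the other way and suggest efficacy after a failed primary test, which the planned interval did not do in the simulations at 18 v 9.

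**Conclusion.** The effect is real, but it is not a defect in the plan. At 18 v 9 and 0.64 v 0.10, a lower limit of exactly 0 accompanies about 5-89% of significant results. The width of that range reflects an unknown distribution of Y, not a known fault. These figures assume the planning rates hold, 10% is lost from each arm, and, except in the unequal-decline and rounded-normal rows, the same share of non-increasers sits at 0 in both arms.

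In every case the limit is conservative and consistent with the test, which alone decides the comparison. Type I error, power and the primary conclusion do not move. The binary quantity the trial was sized on is already reported under SAP 5.3. Tie handling and a footnote explaining a limit of exactly 0 are matters analysts settle routinely in table specifications and coding, which the SAP assigns to the implementation plan. Substituting or adding a dichotomised interval beside the primary test would exchange a cautious mismatch for one that can overstate the result. No change to the SAP is needed.
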